Objectives 
• Primary (Part A and Part B)
– Assess the safety and tolerability of escalating doses of KAN-101 in patients with celiac disease (CeD)• Secondary (Part A and Part B)
– Assess the pharmacokinetics (PK) of KAN-101 after single and multiple doses of KAN-101 in patients with CeD• Exploratory (Part B only)
– Examine the magnitude of the biomarker responses in peripheral blood following gluten challenge (GC)– Assess the incidence of CeD symptoms after a GC	
Methodology 
This is a two-part, multicenter Phase 1 study of KAN-101 in patients with CeD.
 
The 2 parts include:
 
• Part A – First-in-human (FIH) single ascending dose (SAD)	

- Part B – Randomized, placebo (PBO)-controlled, double-blind, multiple ascending dose (MAD)

The study will be conducted in adult patients (≥ 18 years) diagnosed with CeD as demonstrated by intestinal histology and positive serology at the time of diagnosis, who have been following a gluten-free diet (GFD) for > 12 months. Eligible patients must have Human Leukocyte Antigen HLA-DQ2.5 genotype (*HLA-DQA1*05* and *HLA-DQB1*02*) (homozygotes or heterozygotes) since the KAN0009 peptide binds to this major histocompatibility complex (MHC) molecule; patients positive for HLA-DQ8 (*DQA1*03*, *DQB1*0302*) will be excluded, since the KAN0009 peptide does not bind to this MHC molecule.

Part A – SAD

Part A employs a SAD 3+3 design, in which patients will receive a single IV infusion of KAN-101 on Day 1 (D1) followed by 20 days of safety monitoring, which includes assessment of adverse events (AEs), clinical signs and symptoms, and clinical laboratory values.

All cohorts in Part A will employ sentinel dosing, whereby the first patient in each cohort will be dosed at least 7 days prior to the subsequent patients to monitor for the acute and subacute safety of KAN-101.

The doses for Part A include 0.15 mg/kg (Cohort 1), 0.3 mg/kg (Cohort 2), 0.6 mg/kg (Cohort 3), and 1.2 mg/kg (Cohort 4). After the last patient within a given dose cohort has been followed for at least 7 days post-dose, a safety review will be performed by the SMC and will include review of all available safety and PK information. Dosing at the next dose level will only commence upon a recommendation from the SMC and agreement by the Sponsor.

For all patients in Part A, the study will consist of a 28-day screening period, a single dose of KAN-101 administered on D1 followed by a 10-hour monitoring period in the clinic/hospital unit. Patients will be evaluated on D4 (± 1), D8, and D21. In the event that patients are unable to return to the clinic for protocol-specified visits, alternative methods for safety assessments and data collection may be employed to ensure the safety of the trial participant where appropriate. Blood and serum samples will be collected for PK and ADA assessments during the Part A.

Please see [Table 1](#) for the complete schedule of assessments for Part A.

Part B - MAD

Patients enrolled in the double-blind MAD part will be randomized 3:1 to KAN-101 or PBO administered IV for 3 doses. A total of 8 patients per dose cohort (6 KAN-101; 2 PBO) will be enrolled. All cohorts will employ sentinel dosing, whereby the first 2 patients (1 KAN-101 and 1 PBO) in each cohort will be dosed at least 14 days prior (ie, 7 days from third and final dose) to the subsequent patients being dosed to monitor for the acute and subacute safety of multiple doses of KAN-101.

The first MAD cohort (Cohort 5) will begin dosing after the safety review of the SAD Cohort 2 is completed. In Part B, the doses will be administered every 3 days, for a total of 3 doses, and the patients followed for approximately 28 days after the first dose. The planned Part B doses are 0.15 mg/kg, 0.3 mg/kg, and 0.6 mg/kg.

For all cohorts in Part B, after the last patient dosed within a given cohort has been followed for at least 14 days, a safety review will be performed by the SMC. Dosing in the next cohort will commence upon recommendation by the SMC and approval by the Sponsor.

A GC will be initiated on D15 to assess patients' T-cell response to gluten. For the GC, patients will self-administer 9 g of gluten protein orally (PO) on D15, D16, and D17, at approximately the same time each day. CCI

For all patients in Part B, the study will consist of a screening period of up to 28 days, followed by 3 doses of KAN-101 or PBO administered on D1, D4, and D7. The first dose on D1 is followed by a 10-hour monitoring period in the clinic/hospital unit, after which patients will return home before returning on D4 and D7 for the second and third doses, respectively. The D4 and D7 doses will be followed by a 4-hour monitoring period in the clinic. Patients will return to the clinic on D15 to initiate GC and D21 for biomarker sample collection. Patients will have a follow-up phone call on D28. In the event that patients are unable to return to the clinic for protocol-specified visits, alternative methods for safety assessments and data collection may be employed to ensure the safety of the trial participant where appropriate.

Based on data obtained during both the SAD and MAD parts of the study, the protocol may be amended to explore additional dose levels and dosing schedules if supported by the data and recommended by the SMC and approved by the Sponsor.

Please see [Table 2](#) for the complete schedule of assessments for Part B.

Number of Patients (Planned)

It is anticipated that the study will enroll approximately 36 patients. Part A (SAD) will enroll approximately 12 to 24 patients using a 3+3 dose escalation design without intra-patient dose escalation. Part B (MAD) will enroll approximately 24 patients across 3 dose cohorts (6 active patients per cohort). A sample size of 6 patients treated with KAN-101 per cohort in Part B allows for an 0.80 power to detect a treatment-related AE occurring at an event rate of 0.25.

In Part A, patients may be replaced if they do not receive the full dose of study drug or do not complete the D8 visit, as long as they did not discontinue the study due to an AE assessed as related to KAN-101. In Part B, patients may be replaced if they do not receive the full 3 doses of study drug or do not complete the D21 visit, as long as they did not discontinue the study due to a DLT assessed as related to KAN-101.

Starting Dose and Dose Escalation

The initial starting dose of KAN-101 in the Protocol version 2.0 was 1.5 mg/kg, a dose level consistent with an expected efficacious dose and supported by findings from the Good Laboratory Practice (GLP) toxicology studies. Due to non-serious adverse events observed in one patient at the 1.5 mg/kg dose level, the protocol has been amended to start at the dose of 0.15 mg/kg, 10-fold lower than the dose which induced symptoms consistent with gluten ingestion in celiac patients.

Part A will use a 3+3 design to evaluate escalating single doses of KAN-101. Approximately 12 to 24 patients are anticipated for enrollment in Part A. At any dose level, if none of the first 3 patients experiences a dose-limiting toxicity (DLT) (defined as any \geq Grade 3 AE assessed as related to KAN-101 or any Grade 2 AE assessed as related to KAN-101 not resolving within 14 days) then escalation to the next dose level may proceed if recommended by the SMC and approved by the Sponsor. If 1 of the first 3 patients experiences a DLT, the dose level will expand to a maximum of 6 patients if recommended by the SMC. If no DLT occurs among the 3 additional patients enrolled at that dose level, then escalation to the next dose level may proceed if recommended by the SMC and approved by the Sponsor.

Any DLT experienced during the study will result in study pause and review by the SMC. Any \geq Grade 4 AE will result in notification of the FDA in parallel with the SMC and study dosing and enrollment will be paused pending review by FDA. The non-tolerated dose (NTD) is the dose level at which 2 or more patients experience a DLT during the dose escalation safety monitoring period. The maximum tolerated dose (MTD) will be defined as the dose level immediately below the NTD. Of note, dose escalation may not identify an NTD or MTD.

Safety Monitoring Committee

This study will utilize an SMC that will meet regularly to review all accumulated data, including safety and PK (when available) during dose escalation. The SMC will recommend all dose escalation decisions, and/or any changes to the dosing paradigm based on review of the received data. The SMC will also make recommendations about the dose(s) selected for Part B. The Sponsor will make all final decisions related to the doses and regimens examined in this study.

Inclusion Criteria

1. Adults aged 18 to 70 years inclusive
2. Diagnosed with CeD based on positive serology (eg, tissue transglutaminase IgA antibody [tTG-IgA] and/or deamidated gliadin peptide IgG [DGP-IgG]) and intestinal histology consistent with \geq Marsh Type II or with evidence of villous atrophy
3. Has HLA-DQ2.5 genotype (*HLA-DQA1**05 and *HLA-DQB1**02) (homozygotes or heterozygotes)
4. Has followed a GFD for > 12 months immediately prior to study entry

5. Negative or weak positive for transglutaminase (tTG) IgA and negative or weak positive for DGP-IgA/IgG during screening
6. Male or female. Females of childbearing potential must use at least 2 acceptable birth control methods
7. Capable of understanding and complying with protocol requirements
8. Patient understands and has signed the informed consent form (ICF)

Exclusion Criteria

1. Refractory CeD
2. Selective IgA deficiency
3. Positive for HLA-DQ8 (*DQA1*03, DQB1*0302*)
4. Previous treatment with tolerance-inducing therapies for CeD
5. Known wheat allergy
6. **Part B only:** History of hyperacute (requiring medical treatment) or prolonged symptoms (> 48 hours) following gluten exposure
7. Has active inflammatory bowel disease (eg, Crohn's disease, colitis)
8. Presence of other autoimmune disorders in addition to CeD, including but not limited to type 1 diabetes, rheumatoid arthritis, psoriasis, autoimmune thyroid disease, etc.
9. Uncontrolled or significant medical conditions (including active infections or chronic hepatitis) which, in the opinion of the Investigator, preclude participation
10. Patients with clinical signs and symptoms consistent with COVID-19 (eg, fever, dry cough, dyspnea, sore throat, and fatigue) or confirmed infection by appropriate laboratory test within the last 4 weeks prior to screening or on admission

Note: Patients who experienced symptoms consistent with COVID-19 or confirmed infection during the screening period (ie, after signing the ICF but before dosing) may be rescreened after 4 weeks
11. Patients with a prior severe course of COVID-19 requiring extracorporeal membrane oxygenation (ECMO) or mechanical ventilation
12. Receipt of chronic, systemic non-biologic immunosuppressive or immunomodulatory therapies within the last 3 months (eg, methotrexate, sulfasalazine, or corticosteroids such as prednisone, etc.)
13. Positive for HIV, HBV, or HCV
14. Receipt of any vaccination within 4 weeks prior to first dose of study drug
15. Receipt of biologic immunosuppressive or immunomodulatory therapies within the last 12 months (eg, adalimumab, etanercept, certolizumab, etc.)
16. Has any of the following laboratory parameters at Screening:
 - a. Hemoglobin < 10 g/dL

- b. Platelet (PLT) count $< 100 \times 10^9/L$
- c. White blood cell count (WBC) outside the normal range and assessed as clinically significant by the Investigator
- d. Alanine aminotransferase (ALT), aspartate aminotransferase (AST), or alkaline phosphatase (ALP) $> 1.5 \times$ the upper limit of normal (ULN)
- e. Estimated glomerular filtration rate (eGFR) $\leq 60 \text{ mL/min/1.73 m}^2$ based on the Cockcroft-Gault equation during screening

17. Average alcohol consumption of > 2 drink-equivalents per day

18. History of dermatitis herpetiformis

19. Pregnant or breastfeeding

Investigational Product, Dosage, and Mode of Administration

CCI

Administration will be by IV infusion over approximately 30 minutes.

For Part A, patients will receive a single IV infusion of KAN-101.

For Part B, patients will receive a total of 3 IV infusions of either KAN-101 or PBO, with each of the doses administered on D1, D4, and D7. All doses will be prepared as outlined in the Pharmacy Manual by an unblinded pharmacist.

Study Duration

The maximum duration of study participation for patients in Part A is approximately 49 days, which includes a screening period of up to 28 days, followed by a single dose of KAN-101 on D1, and a 3-week follow-up period.

The maximum duration of study participation for patients in Part B is approximately 56 days, which includes a screening period of up to 28 days, followed by 3 doses of KAN-101 each administered on D1, D4, and D7, a GC on D15 to D17, assessment on D21, and a final phone call on D28.

Assessment of Safety

Safety will be assessed through the monitoring of AEs, clinical signs and symptoms, vital signs, and clinical laboratory evaluations.

Patients will be monitored continuously for AEs from screening until the final Safety Follow Up Visit on D21 (Part A) or final phone call on D28 (Part B). AE severity will be assessed using the National Cancer Institute Common Terminology Criteria for Adverse Events (NCI-CTCAE) v5.0 or higher.

In relation to patient safety during the COVID-19 pandemic, current national laws and local recommendations should be strictly adhered to during the study.

Patient safety will be evaluated during Part A (SAD) and Part B (MAD) to determine dose escalation. The dose escalation safety monitoring period in Part A is from the single IV administration of KAN-101 through the D8 clinic visit. The dose escalation safety monitoring period in Part B is from the first IV administration of KAN-101 or PBO through the D15 clinic visit, prior to initiating the GC.

In both parts, patients will be monitored in the clinic for 10 hours following the first IV administration KAN-101 or PBO. In Part B patients will be monitored in the clinic for 4 hours following completion of the second and third IV infusion of KAN-101 or PBO.

Any DLT experienced during the dose escalation safety monitoring period will result in a pause in the study enrollment and a review of all the available safety data by the SMC prior to dosing any additional patients on either part of the study. Any \geq Grade 4 AE will result in notification of the FDA in parallel with the SMC and study dosing and enrollment will be paused pending review by FDA.

Primary Endpoint (Part A and Part B)

- Incidence and severity of treatment-emergent AEs (TEAEs) as assessed by the CTCAE v5.0

Secondary Endpoint (Part A and Part B)

- Plasma concentrations and PK parameters of KAN-101

Exploratory Endpoints (Part B only)

CCI

Pharmacokinetics

In Part A and Part B, samples for PK assessment will be collected according to the schedules outlined in [Table 1](#) and [Table 2](#). Part A and Part B will be analyzed separately and together.

Statistical Methods

Statistical methods will be descriptive. No hypothesis will be formally tested. For Part A, the data will be listed by dose level. For Part B, summary statistics will be provided by dose level. Categorical variables will be summarized using numbers and percentages. Continuous variables will be summarized by total number (n), mean, standard deviation (StD), median, and range (minimum and maximum).

Part A and Part B will be analyzed separately and together.

A formal statistical analysis plan (SAP) will be developed and finalized prior to study database lock.

Table 1: Schedule of Assessments Part A (SAD)

Assessment	Screening	Study Period				Early Term.
Study Day	-28	1	4 (±1)	8	D21 (±1)	
Screening Assessments						
Informed Consent	X					
Medical History & Demographics	X					
Disease History	X					
Inclusion/Exclusion	X					
ECG	X	X ²		X		
HIV, HBV, HCV testing	X					
HLA Genotype and CeD Serology ¹	X					
Clinical Procedures						
Physical Examination	X ³					X
Pregnancy Test ⁴	X	X ⁵				
Vital Signs ⁶	X	X ⁵		X		
Con Meds/Procedures, Incidental Gluten Exposure	X	X	X	X	X	X
Safety Assessments						
Adverse Events	X	X ⁷	X	X	X	X
Lab Tests (Safety)	X	X ⁵	X	X		X
Study Drug Administration						
KAN-101 Administration		X				
Additional Blood Samples						
PK Blood Sample		X ⁸				
ADA Serum Sample		X ⁵			X	X

¹ All patients will be assessed via central laboratory for HLA genotype and CeD serology (eg, tTG-IgA and DGP-IgG) at screening to confirm eligibility. For rescreening, HLA does not need to be repeated and CeD serology only needs to be repeated if >3months have elapsed from last assessment.

² ECG performed pre dose (at least 5 min before infusion), 20(±5) min after start of infusion, and 1 hour (±10 min) post infusion

- ³ Includes weight and height at screening only.
- ⁴ Pregnancy test at screening must be serum; serum or urine tests are acceptable on D1 prior to dosing.
Pregnancy test must be negative before study drug is administered.
- ⁵ Samples/Measurements taken pre-dose (at least 5 min prior to infusion).
- ⁶ Vital signs (pulse rate, temperature, diastolic and systolic BP).
- ⁷ On D1 patients will be observed in the clinic/hospital unit for 10 h after initiation of IV infusion and followed up with by phone approximately 24 hours after dosing.
- ⁸ PK samples to be taken pre-dose (at least 5 min prior to infusion) and the following timepoints after the end of infusion: 0 (+2) min, 7 (\pm 2) min, 15 (\pm 2) min, 30 (\pm 5) min, 1 h (\pm 5 min), 2 h (\pm 5 min), 3 h (\pm 5 min), 4 h (\pm 5 min) and 6 h (\pm 5 min).

Abbreviations: ADA = anti-drug antibody; BB = blood pressure; CeD = celiac disease; Con Meds = concomitant medications; ECG = electrocardiogram; Early Term. = early termination; HBV = hepatitis B; HCV = hepatitis C; HIV = human immunodeficiency virus; HLA = Human Leukocyte Antigen; PK = pharmacokinetics; SAD = single ascending dose.

Table 2: Schedule of Assessments Part B (MAD)

Assessments	Screening	Treatment Period			PD Assessment		Follow-up ¹	Early Term.
		1	4	7	15	21		
Study Day	-28	1	4	7	15	21	28 (±3)	
Screening Assessments								
Informed Consent	X							
Medical History & Demographics	X							
Disease History	X							
Inclusion/Exclusion	X							
ECG	X	X ²		X ²	X ¹⁵			
HIV, HBV, HCV testing	X							
HLA Genotype and CeD Serology ³	X							
Clinical Procedures								
Physical Exam	X ⁴							X
Pregnancy Test ⁵	X	X ⁶	X ⁶	X ⁶				
Vital Signs ⁷	X	X ⁶			X			
Con Meds/Procedures, Incidental Gluten Exposure	X	X	X	X	X	X	X	X
3-Day GC					X ⁸			
Safety Assessments								
Adverse Events	X	X ¹⁰	X ¹⁰	X ¹⁰	X	X	X	X
Lab Tests (Safety)	X	X ⁶	X ⁶	X ⁶	X			X
Study Drug Administration								
KAN-101/PBO Administration		X	X	X				
Additional Blood Samples								
PK Blood Sample		X ¹¹	X ⁶	X ¹²	X ¹⁵			
ADA Sample		X ⁶				X		X

CCI

CCI

Assessments	Screening	Treatment Period			PD Assessment		Follow-up ¹	Early Term.
		1	4	7	15	21		
Study Day	-28	1	4	7	15	21	28 (±3)	

CCI

- ¹ Phone call.
- ² ECG performed pre dose (at least 5 min before infusion), 20(±5) min after start of infusion, and 1 hour (±10 min) post infusion
- ³ All patients will be assessed via central laboratory for HLA genotype and CeD serology (eg, tTG-IgA and DGP-IgG) at screening to confirm eligibility. For rescreening, HLA does not need to be repeated and CeD serology only needs to be repeated if >3months have elapsed from last assessment.
- ⁴ Includes weight and height at screening only.
- ⁵ Pregnancy test at screening must be serum; serum or urine tests are acceptable predose on D1, D4, and D7. Pregnancy test must be negative before each dose of study drug is administered.
- ⁶ Samples/Measurements taken pre-dose (at least 5 min prior to infusion).
- ⁷ Vital signs (pulse rate temperature, diastolic and systolic BP).
- ⁸ The GC will consist of patients self-administering 9 g of gluten protein PO for each of 3 days (D15 to D17), with the first administration in the clinic on D15. GC should be administered at approximately the same time each day.
- ⁹ CCI
- ¹⁰ On D1 patients will be observed in-clinic for 10 h from the start of IV infusion and followed up with by phone approximately 24 hours after dosing; on D4 and D7 (dosing days) patients will be observed for 4 h in clinic from the start of IV infusion.
- ¹¹ PK samples to be taken at pre-dose (at least 5 min prior to infusion) and the following timepoints after the end of infusion: 0 (+2) min, 7 (±2) min, 15 (±2) min, 30 (±5) min, 1 h (±5 min), 2 h (±5 min), 3 h (±5 min), 4 h (±5 min) and 6 h (±5 min).
- ¹² PK samples to be taken at pre-dose (at least 5 min prior to infusion) and the following timepoints after the end of infusion: 0 (+2) min, 7 (±2) min, 15 (±2) min, 30 (±5) min, 1 h (±5 min), 2 h (±5 min), and 4 h (±5 min).
- ¹³ CCI
- ¹⁴ CCI
- ¹⁵ Collected prior to oral gluten challenge

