4.2. PART B – Multiple Ascending Dose

Part B will be initiated following successful completion and SMC review of SAD Cohort 2 in Part A. This transition at Cohort 2 from single to multiple dosing of KAN-101 is supported by nonclinical models that show clearance of KAN-101 within 24 hours, and in vivo animal studies that did not show any drug accumulation when KAN-101 was given 3 times a week.

Part B employs a randomized, double-blind multiple ascending dose (MAD) design, in which 3 cohorts of patients will be assigned 3:1 to either KAN-101 or matching placebo (PBO). Patients in Part B will receive an IV infusion of KAN-101 or PBO on D1, D4, and D7. All cohorts in Part B will employ sentinel dosing, whereby the first 2 patients (1 KAN-101 and 1 PBO) in each cohort will be dosed at least 14 days prior to the subsequent patients (ie, 7 days following the third and final dose) to monitor for the acute and subacute safety of KAN-101.

The doses for Part B include 0.15 mg/kg (Cohort 5), 0.3 mg/kg (Cohort 6), and 0.6 mg/kg (Cohort 7). After the last patient dosed within a given cohort has been followed for at least 14 days, a safety review will be performed by the SMC. Initiation of the next dose cohort will commence upon recommendation by the SMC after review of available safety and PK data and approval of the Sponsor.

For all patients in Part B, the study will consist of a screening period of up to 28 days, followed by 3 doses of KAN-101, each administered on D1, D4, and D7. The first dose on D1 will be followed by a 10-hour monitoring period in the clinic/hospital unit and a phone call follow up approximately 24 hours after dosing. Subsequent doses scheduled on D4 and D7 have a 4-hour monitoring period in the clinic/hospital unit.

- If a patient is experiencing active AE(s) which require clinical monitoring at the end of the clinic/hospital unit monitoring period, the patient should not be discharged and should be followed until satisfactory resolution as determined by PI
- If feasible, patients should be advised to have someone stay with them after discharge until 24 hours have elapsed after study drug administration on D1.
- If patients do not live within 1-hour travel time of an emergency medical facility, they should remain in the clinic/hospital unit for the first 24 hours after study drug administration.
- Patients should be instructed not to drive themselves to seek emergency medical treatment.

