4.7. Dose Escalation Safety Period

In Part A, the dose escalation safety monitoring period is from the beginning of IV administration through D8. Any AEs that meet the above criteria but occur after the dose escalation safety monitoring period of Part A may be considered by the SMC in the evaluation for Part B dose selection.

The dose escalation safety monitoring period in Part B is from the beginning of the first IV administration of KAN-101/PBO through the D15 clinic visit, prior to initiating the GC.

The length of the monitoring periods for safety review is supported by nonclinical exposure data, suggesting KAN-101 will have cleared 5 half-lives, and nonclinical animal model data demonstrating that the tolerance induction mechanism can develop within 1 week of dosing. AEs and any abnormal clinical parameters, including laboratory findings, observed during this period will be used by the SMC to determine whether dose escalation should proceed.

No patient with a DLT will be replaced.

In both parts, patients will be monitored in the clinic for 10 hours following the first IV administration of KAN-101/PBO. In Part B, patients will be monitored in the clinic for 4 hours following completion of their second and third dose.

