9. CC [REDACTED]
10. On D1 patients will be observed in-clinic for 10 h from the start of IV infusion and followed up with by phone approximately 24 hours after dosing; on D4 and D7 (dosing days) patients will be observed for 4 h in clinic from the start of IV infusion.
11. PK samples to be taken at pre-dose (at least 5 min prior to infusion) and the following timepoints after the end of infusion: 0 (+2) min, 7 (±2) min, 15 (±2) min, 30 (±5) min, 1 h (±5 min), 2 h (±5 min), 3 h (±5 min), 4 h (±5 min), 6 h (±5 min).
12. PK samples to be taken at pre-dose (at least 5 min prior to infusion) and the following timepoints after the end of infusion :0 (+2) min, 7 (±2) min, 15 (±2) min, 30 (±5) min, 1 h (±5 min), 2 h (±5 min), and 4 h (±5 min).

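### Table 2 footnote 10 starts the 4 h Day 4/Day 7 observation at the start of infusion, Section 4.7 at its completion; among visible rows the half-hour shortfall falls on Day 4

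*Protocol*

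**What the plan says.** The Part B observation period after doses 2 and 3 is described in six places.

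- **Protocol Table 2, footnote 10** (attached to the adverse event row): "on D4 and D7 (dosing days) patients will be observed for 4 h in clinic from the start of IV infusion".
- **SAP Table 9, footnote 10** has the same clock: "patients will be observed for 4 h in clinic from the start of IV infusion".
- **Protocol Section 4.7:** "In Part B, patients will be monitored in the clinic for 4 hours following completion of their second and third dose".
- **Protocol synopsis, Assessment of Safety:** "In Part B patients will be monitored in the clinic for 4 hours following completion of the second and third IV infusion".
- **Protocol synopsis, Part B methodology:** "The D4 and D7 doses will be followed by a 4-hour monitoring period in the clinic". This fits a period that begins once the dose is in, but names no clock.
- **Protocol Section 4.2:** "Subsequent doses scheduled on D4 and D7 have a 4-hour monitoring period in the clinic/hospital unit". This gives a length and no clock.

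Section 10.2 sets the infusion at about 30 minutes. Table 2, footnote 12, schedules the last Day 7 PK sample 4 h (±5 min) after the end of infusion. On Day 4 the PK, safety laboratory and pregnancy entries carry pre-dose footnotes, and the ECG and vital-signs cells are blank.

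**The concern.** Start and completion of an infusion are different moments, so footnote 10 and Section 4.7 cannot both define the same four hours. The difference equals the infusion's duration. All of this is current text; none of it comes from the amendment history.

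Sites commonly work from the schedule of assessments, and here the schedule is the less protective text. A site following footnote 10 could release a patient before Section 4.7 allows, and it would be unclear whether that release is a protocol deviation. Day 4 is the first repeat dose in a first-in-human study whose starting dose was cut tenfold after one patient had symptoms. Section 1.2 also reports that celiac-like symptoms with a different, non-targeted peptide product began within hours of administration. The footnote's follow-up telephone call at about 24 h is tied to Day 1 only.

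**Working it through.** The plan states no figure for this gap, so there is none to reproduce. The check is timing arithmetic.

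**Inputs**

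- Observation period: 4 h = 240 min (all six texts).
- Infusion duration: 30 min (Section 10.2).
- Last Day 7 PK sample: 240 ± 5 min after the end of infusion (Table 2, footnote 12).
- Part B size: 24 patients, 18 KAN-101 and 6 placebo, in 3 cohorts of 8 (Section 12.1 and synopsis).

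**Step 1. Release time under each text, uninterrupted infusion**

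| Text | Earliest release, from start | Time observed after end of infusion |
|---|---|---|
| Table 2, footnote 10 | 240 min | 240 − 30 = 210 min (3.5 h) |
| Section 4.7 and synopsis | 30 + 240 = 270 min | 240 min (4.0 h) |

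Gap: 270 − 240 = 30 min, or 30/240 = 12.5% of the intended period.

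**Step 2. Day 7**

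The last PK draw falls between 30 + 235 = 265 min and 30 + 245 = 275 min from the start. The patient must be present for it. Against the 270 min in Section 4.7, the remaining gap is at most 270 − 265 = 5 min. Because the sample is timed from the end of infusion, this bound holds for any infusion duration. It would widen only if that sample were moved earlier; Section 12.9 allows sampling times to change. The sample also supports the completion clock, since Table 2 itself keeps the Day 7 patient beyond footnote 10's release time.

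**Step 3. Day 4**

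No visible row places a timed procedure after the infusion, so nothing visible holds the patient past 240 min from the start. The full 30 min gap remains. Reach: 3 × 8 × 1 = 24 planned Day 4 infusions, 18 of them KAN-101. Section 4.2 allows replacement of Part B patients, so the number can exceed 24.

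**Step 4. Slowed infusion (nominal clock only)**

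Section 10.5 slows the infusion to 50% or less of the original rate after a Grade 2 reaction. Assuming exactly half rate from minute *t*, the infusion ends at *t* + 2(30 − *t*) = 60 − *t* min, and footnote 10 leaves 240 − (60 − *t*) = 180 + *t* min.

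- *t* = 0: 180 min (3.0 h).
- *t* = 15: 195 min (3.25 h).
- *t* = 30: 210 min (3.5 h).

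This range holds only for exactly half rate. A slower rate or an interruption would leave less on the footnote's clock.

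**Step 5. Clinic time added by the fix**

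24 × 0.5 h = 12 patient-hours on Day 4 for the planned patients with uninterrupted infusions.

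**The case against.** The best case against the point is that it is editorial. The gap is 30 minutes on one dosing day, in a patient already observed for 10 h on Day 1 and telephoned at about 24 h, within cohorts that use sentinel dosing. Protocol Amendment 4 gives a plasma half-life under 20 minutes as a rationale, so 3.5 h covers more than 210/20 = 10.5 half-lives. No text orders discharge at four hours from the start, and staying four hours after completion satisfies every version. Much of this stands. The half-life argument concerns exposure, however, and does not exclude delayed immune symptoms.

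Other rules also narrow the effect. Section 4.2 bars discharge while an active adverse event needs clinical monitoring. It also asks patients living more than an hour from emergency care to remain for 24 h after study drug; that bullet names no particular dosing day, so as written it covers Day 4.

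A reader might infer from Step 4 that patients who react are released earliest. The documents do not support that. For a Grade 2 reaction, Section 10.5 calls for increased vital-sign monitoring until the patient is stable, and the Section 4.2 discharge bar applies as well. The slowed-infusion figures are differences between clocks, not expected discharge times. Nor does the 2 h infusion that Section 10.5 describes after a Grade 3 reaction make a 2 h gap likely: if related to KAN-101, that reaction is a dose-limiting toxicity, and Section 4.9 then stops further doses to that patient in Part B.

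The Day 4 attribution has a limit. Table 2 has redacted rows and footnotes, and one of them could hold a post-infusion Day 4 procedure. Finally, the SAP governs analysis, not clinic discharge, and its version 3.0 (12 November 2021) postdates the planned last visit of June 2021. Correcting the SAP copy is for consistency only.

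**Conclusion.** The contradiction holds. Footnote 10 permits release 3.5 h after an uninterrupted 30 min infusion, where Section 4.7 and the synopsis require 4.0 h. The completion clock is the better-supported reading: two texts state it outright, the Part B methodology text fits it, and the Day 7 PK schedule is consistent with it.

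A reader might take the shortfall to apply equally to both repeat doses, or to weaken the primary safety endpoint. Neither is supported. On Day 7 the gap is about 5 min at most as the sampling now stands, and adverse events are collected through the Day 28 call whichever clock is used. No endpoint, dose-limiting toxicity rule, sample size or analysis changes.

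What remains is a small operational safety inconsistency on Day 4, worth correcting but of low weight. Confidence is high for the conflict in wording. Placing its effect on Day 4 assumes that the redacted rows contain no post-infusion Day 4 procedure. The 30 min size assumes an uninterrupted infusion of the planned length.

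**What to change.** In protocol Table 2, footnote 10, change the Day 4/Day 7 clause to read: for 4 h in clinic after the end of IV infusion. Make the same change in SAP Table 9, footnote 10. Leave the Day 1 10 h clock as it is; the footnote will then carry a start clock for Day 1 and an end clock for Days 4 and 7, so both should be stated explicitly.

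The cost is one phrase in two footnotes. Sites that have been using the footnote clock would add about 0.5 h of clinic time per uninterrupted Day 4 infusion, roughly 12 patient-hours for the 24 planned patients and somewhat more with replacements, plus up to about 5 min per patient on Day 7.
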